## List of Abbreviations

Abbreviation or specialist term	Evaluation			
AE	Explanation Adverse Event			
BP				
BUN	Blood Pressure			
	Blood Urea Nitrogen			
CBC	Complete Blood Count			
CFR	Code Of Federal Regulations			
CI	Confidence Interval			
CNS	Central Nervous System			
CRF	Case Report Form			
CRT	Chemoradiation Treatment			
CTCAE	Common Terminology Criteria For Adverse Events			
DSMC	University of Virginia Cancer Center Data and Safety Monitoring Committee			
ECG	Electrocardiogram			
FDA	Food And Drug Administration			
GCP	Good Clinical Practices			
HCG	Beta-Human Chorionic Gonadotropin			
HR	Heart Rate			
I/E	Inclusion Exclusion Criteria			
ICH	International Conference On Harmonization			
IND	Investigational New Drug Application			
INR	International Normalized Ratio			
IRB	Institutional Review Board			
iULN	Institutional Upper Limit Of Normal			
IV	Intravenous			
OS	Overall Survival			
PFS	Progression Free Survival			
RR	Clinical response rate			
pCR	Pathological complete response			
aPTT	Activated Partial Thromboplastin Time			
PT	Prothrombin Time			
SAE	Serious Adverse Event			
US	United States			
UVA	University of Virginia			
WOCBP	Women of Childbearing Potential			

# 1.0 TRIAL SUMMARY

Abbreviated Title	Chemoradiation (CRT) with pembrolizumab in Cervical Cancer			
Trial Phase	Phase 2			
Clinical Indication	Locally advanced cervical cancer (stages IB-IVA, all histologies)			
Trial Type	Randomized			
Type of control	Active comparator and historical data			
Route of administration	IV			
Trial Blinding	Unblinded (open label)			
Treatment Groups	2 arms			
Number of trial subjects	88 evaluable			
Estimated enrollment period	24 months			
Estimated duration of trial	3 years to analysis of primary endpoint			
Duration of Participation	20 weeks active treatment plus 5 years survival follow-up			

#### 2.0 TRIAL DESIGN

## 2.1 Trial Design

This is a randomized, Phase II, open-label multi-center study in which 88 eligible subjects with locally advanced cervical cancer will be treated with standard chemoradiation treatment (CRT) plus the PD-L1 monoclonal antibody pembrolizumab. The primary objectives in the study will be to estimate the safety and immune response to pembrolizumab given either sequentially or concurrently with CRT. Secondary objectives will evaluate the metabolic response and rates of distant metastases following treatment with pembrolizumab given sequentially or concurrently with CRT. The study design also affords the opportunity to characterize the effect of treatment on immune response pathways by estimating the effects of treatment on specific immune markers.

At baseline, subjects will undergo a full medical history and physical examination, vital signs, performance status, and general laboratory evaluations. Baseline imaging assessments will include PET/CT and MRI (MRI is required, unless there are contraindications or at the discretion of the investigator). Eligible subjects (n=88) will be randomized 1:1 to two treatment sequences to receive pembrolizumab after completion of CRT (Arm 1) or to receive pembrolizumab concurrent to CRT (Arm 2). Subjects in both arms will receive identical regimen, as follows:

- Chemotherapy: Weekly Cisplatin (40 mg/m^2) for 5 or 6 weeks
- Radiation: Standard dose IMRT with 4-6 fractions of high-dose-rate (HDR) brachytherapy using standard doses and methods
- Pembrolizumab: 200 mg, 3 cycles (every 21 days)

Subjects will be evaluated for safety by monitoring for adverse events. All subjects will have a PET/CT approximately 12 weeks following completion of all CRT to evaluate for response. Tumor and blood samples will be collected at baseline, during CRT and post-treatment for analysis of immune response markers. All subjects will be followed for disease-free survival and overall survival for up to 5 years.

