### 7.1 Evaluation Criteria

## 7.1.1 Safety Endpoints

All patients receiving any protocol treatment will be evaluated for safety. Safety assessments will include:

- i. Incidence and severity of adverse events.
- ii. Incidence of dose limiting toxicities (DLT) defined in section 7.4.

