## 7.2 Sample size and accrual

Results in Jordanova ES, et al 2008, report estimates of CD8+/Treg for normal cervix and cervical cancers tissue for cervical cancer patients who underwent radical hysterectomy with lymphadenectomy.[4] These data provide the assumed "natural baseline" of cancer patients' in this study with CD8+/Tregs being lower in cancer tissue, and results in a Cohen's *d*av effect size (ES) of 0.45. Estimated sample size is based upon being able to detect a similar effect size between CD8+/Tregs at baseline and end of CRT, and baseline to the 12 weeks post CRT assessment without correction for multiple comparisons. Data from Nilges, K et al, 2003, indicates a mean (standard deviation) of 23.32 (15.39) in CD8+/Tregs measured in the tumor infiltrating lymphocytes (TIL) from patients with cervical cancer. Given these data, 44 eligible patients are required (per arm) to assess change in pre/post CD8+/Tregs with an ES of 0.45 with type I and II errors of 10%. Each within arm comparison supports the following hypothesis. Cisplatin can kill T cells, therefore the CRT may eliminate both CD8+ HPV CTL and Tregs, and the ensuing or concurrent pembrolizumab treatment may increase the CD8+/Treg ratio (test that pembrolizumab will increase CD8+/Tregs to an ES of 0.45).

Adjusting for an overall 10% ineligibility/drop-out rate, maximum accrual to the study is estimated at 98 patients. Accrual is estimated at 4 patients a month, thus accrual to the study should be completed by 2.0 years with primary analysis at 3 years.

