## 7.4 Safety and Futility Monitoring

## 7.4.1 Safety monitoring

Dose Limiting Toxicity (DLT) is defined as an adverse event which: i) is determined to be at least possibly related to treatment with pembrolizumab; ii) occurs within the first 30 days after the first pembrolizumab infusion; and iii) meets one of the below criteria:

- Pneumonitis Grade  $\geq$  3
- Any non-hematological toxicity Grade  $\geq$  3, except for the following:
  - Grade 3 toxicity that is expected from standard of care cisplatin and radiation
  - Grade 3 Colitis, hypophisitis, or hyperthyroidism lasting less than 7 days
  - Grade 3 electrolyte toxicities that are corrected to grade 1 or less within 24 hours
  - Grade 3 hypertension that can be controlled with oral medications and does not require treatment delay for > 7 days
  - Grade 3 diarrhea that is not refractory to anti diarrhea medications and is corrected to Grade 1 or less within 48 hours
  - Grade 3 nausea and vomiting that is not refractory to anti-emetic therapy and is corrected to Grade 1 or less within 48 hours
  - Grade 3 rise in creatinine, if corrected to Grade 2 or less after up to 2 liters of intravenous fluids within 24 hours
  - Grade 3 elevation in AST/ALT if < 1.5 times the baseline level
  - Grade 3 elevation of ALP (alkaline phosphatase)
  - Grade 3 hypoalbuminemia
  - o Grade 3 lymphopenia

- Grade 3 rash if it returns to ≤ grade 2 after 1 week of symptomatic treatment
- Any Grade ≥ 4 toxicity
- Other AEs if they are clearly related to pembrolizumab and are causing substantial morbidity for subjects, as determined by the study chair.

Within each arm, safety will be assessed by monitoring the number of patients who experience a DLT. Results reported in ASCO 2015 abstracts [22, 23] for pembrolizumab in combination with other treatments resulted in an overall DLT rate of 1/59=2% with a 90%Cl(1%, 8%). For this study the upper boundary of a sequential probability ratio test (SPRT) based upon a binomial test of proportions for DLT will be used for monitoring to protect against excessive failure rates. The stopping boundary is for a SPRT contrasting a 5% versus 25% DLT rate, with nominal type I and II errors of 10% and 10%, respectively. The slope of the parallel line for monitoring is 1.190 and the intercept is 0.128.

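### Section 2.1 gives the evaluable number (88) as the number randomised, and the DLT stopping rule needs three small repairs: a table that covers 49 per arm, corrected line labels, and its own error rates

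*Combined protocol and SAP*

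**What the plan says.** **Enrolment.** Section 2.1 states that "88 eligible subjects with locally advanced cervical cancer will be treated" and then that "Eligible subjects (n=88) will be randomized 1:1 to two treatment sequences". Section 1.0 gives the number of subjects as 88 evaluable. Section 7.2 says "44 eligible patients are required (per arm) to assess change in pre/post CD8+/Tregs", for an effect size of 0.45 with type I and II errors of 10%. It then allows for 10% ineligibility or drop-out, so that "maximum accrual to the study is estimated at 98 patients". Under 5.7.3, subjects who leave before any treatment do not count as accruals and are replaced.

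**Safety rule.** Section 7.1.1 states: "All patients receiving any protocol treatment will be evaluated for safety". Section 7.4.1 monitors DLTs within each arm against the upper boundary of a sequential probability ratio test (SPRT) of 5% versus 25%, "with nominal type I and II errors of 10% and 10%, respectively". It prints a slope of 1.190 and an intercept of 0.128, and a table whose last row covers 38 to 44 patients in an arm (boundary 7 or more). Crossing in either arm suspends accrual to the whole study pending review.

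**The concern.** Eighty-eight cannot be both the number randomised and the number left after a 10% loss. A site or committee working from 2.1 could close randomisation at 88 and fall short of the evaluable number on which the power statement rests.

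If 7.2 is followed, as the plan appears to intend, about five treated patients per arm lie beyond the last row of the only numerical stopping rule for DLTs. A reader who tries to fill the gap from the printed line finds that it gives impossible values. The error rates quoted to the DSMC also belong to a different procedure, an SPRT with two boundaries and no fixed maximum. The rule in use has one boundary, ends at 44, and runs in two arms.

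**Working it through.** **1. Reproduce 44 and 98.** Inputs from 7.2: effect size 0.45, alpha 0.10, power 0.90, paired pre/post comparison within arm. Sidedness is not stated.
- Normal approximation, two-sided: n = ((1.645 + 1.282)/0.45)² = 42.3.
- Noncentral t, two-sided 10%: n = 44, power 90.2%. This matches the plan.
- Noncentral t, one-sided 10%: n = 34. This does not match, although the wording in 7.2 is directional ("test that pembrolizumab will increase CD8+/Tregs to an ES of 0.45").
- Cross-check on 7.5: a two-sided 10% two-sample t-test with 44 per arm gives 67.3%, 75.2% and 87.4% at effect sizes 0.45, 0.5 and 0.6, against the stated 67%, 75% and 87%. The two-sided reading is therefore used below.
- Inflation: 88/0.9 = 97.8, so 98, or 49 per arm. This also matches.

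**2. Power under each total, with the full 10% lost.**

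| Enrolled | Remaining | Per arm | Within-arm power |
|---|---|---|---|
| 88 | 88 × 0.9 = 79.2 | 39–40 | 86.8%–87.5% |
| 98 | 98 × 0.9 = 88.2 | 44 | 90.2% |

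**3. The SPRT line.** Inputs from 7.4.1: p0 = 0.05, p1 = 0.25, alpha = beta = 0.10.
- D = ln[p1(1−p0)/(p0(1−p1))] = ln[(0.25 × 0.95)/(0.05 × 0.75)] = ln 6.333 = 1.846.
- Slope = ln[(1−p0)/(1−p1)]/D = ln(0.95/0.75)/1.846 = 0.236/1.846 = 0.128.
- Intercept = ln[(1−beta)/alpha]/D = ln 9/1.846 = 2.197/1.846 = 1.190.

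The two printed constants are right but their labels are exchanged. As labelled, the boundary at 44 patients would be 0.128 + 1.190 × 44 = 52.5 DLTs, more than the number of patients. With the labels corrected, 1.190 + 0.128n rounded up reproduces every printed row.

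**4. Extending the table on the corrected line.** At n = 45 the line is 6.95, so 7 or more. At n = 46 it is 7.08 and at n = 49 it is 7.46, so 8 or more. It is 7.98 at n = 53, so a boundary of 8 holds to there.

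**5. Exact crossing probabilities per arm.** These come from a recursion over patients using the printed boundaries, and then using the extended ones.

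| True DLT rate | Table ending at 44 | Extended to 49 |
|---|---|---|
| 5% (false stop) | 6.28% | 6.33% |
| 25% (detection) | 97.1% | 97.8% |

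Missed detection at 44 is 100 − 97.1 = 2.9%. With two independent arms both at a 5% DLT rate, the chance that at least one crosses by 44 is 1 − (1 − 0.0628)² = 12.2%. At 49 it is 1 − (1 − 0.0633)² = 12.3%.

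**The case against.** A reader might infer that the plan has two competing sample sizes and that a stated property fails under either. The documents do not support that. Section 1.0 calls 88 evaluable, 7.2 uses the same number and the same word (eligible) for its post-loss target, and 7.2 carries out the inflation correctly. The power claims in 7.2 and 7.5 are conditional on 44 eligible per arm and hold at 98. The 87% is also a worst case: the 10% covers ineligibility as well as drop-out, and 2.1 already calls its 88 eligible, so taking off the full 10% may count ineligibility twice. The plan does not give the split.

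On the table, the missing rows hardly change the rule's behaviour. The rule acts by suspending accrual, and patients 45 to 49 are the last to enter. At 4 patients a month (about 2 per arm), five more per arm take about 2.5 months, or some 11 weeks. In Arm 1, pembrolizumab starts in Week 9 and the DLT window is 30 days, so the 44th patient is not assessable for about 12 weeks, when accrual would be essentially over. Arm 1 patients lost during CRT never start pembrolizumab and cannot have a DLT as defined, so fewer than 49 may be at risk there. The DSMC also reviews aggregate adverse events monthly (6.4.5.1).

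A reader might also infer that the quoted error rates mislead the DSMC about protection. But 7.4.1 calls them nominal, discloses that only the upper boundary is used, and claims no study-wide rate. The true per-arm errors are both better than 10%, and crossing leads to review, not automatic closure.

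All of this stands, and it limits the size of the point. It does not remove the wrong label in 2.1, the missing rows, or the exchanged constants.

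**Conclusion.** The point holds as a minor correction. Section 2.1 names the post-loss target as the number randomised and treated. The consequence, power of about 87% instead of 90%, arises only if 2.1 is followed literally and the full 10% is lost. It rests on the two-sided 10% paired t-test that reproduces 44. Under a one-sided test, power at 39–40 would be 93–94%, but that test does not yield the plan's sample size.

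At 98 accrued, up to about five treated patients per arm have no printed DLT boundary. The figure of 49 is the 1:1 share of 98; blocking within site can put an arm slightly above it. Operating characteristics move by less than one percentage point at either design rate. The exchanged slope and intercept are a plain error and are the reason the gap cannot be closed from the text as printed. The rule's actual errors at 44 are about 6.3% false stop and 2.9% missed detection per arm. The study-level false suspension of about 12% assumes independent arms and contradicts no stated figure; it is information the plan does not supply.

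**What to change.** - **Section 2.1:** state that up to 98 patients (about 49 per arm) are randomised to give 88 evaluable, not counting those replaced under 5.7.3 because they left before any treatment. Section 1.0 can carry the same sentence beside its evaluable number.
- **Section 7.4.1, line:** correct the labels to slope 0.128 and intercept 1.190.
- **Section 7.4.1, table:** change the last row to 38–45 patients, 7 or more, and add 46–49 patients, 8 or more. The added row may be written to 53 to cover an arm that blocking takes above 49.
- **Section 7.4.1, error rates:** beside the nominal 10%/10%, report the exact figures for the rule as used: about 6.3% false stop and 97.8% detection per arm at 49, and about 12% false suspension for the study with independent arms.

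The cost is a few lines of protocol text, one revised table row and one added row. No patients are needed beyond the 98 already planned.

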#### Figure 1. Study Design

[figure not shown]
[figure not shown]

Figure 2. Study Schema

Protocol/Amendment No.: UVA-LACC-PD201, Version 4.0, 06 March 2018

## 3.0 OBJECTIVES & HYPOTHESES

#### 3.1 Primary Objectives

- (1) To estimate the immunologic effects, as assessed in the tumor & PBMC, of both sequential and concurrent administration of pembrolizumab to CRT. Change between pre and post measurements of HPV E2, E7 specific CD8+ T cells, regulatory FoxP3+ T cells (Tregs) and the ratio of CD8+ T cells to Tregs are the immune measurements of primary interest.
- (2) To determine the safety of concurrent chemoradiation in combination with pembrolizumab for the treatment of locally advanced cervical cancer.

#### 3.2 Secondary Objectives

- To estimate rates of complete metabolic response on PET/CT imaging obtained 12 weeks after CRT.
- (2) To estimate rates of distant metastasis as the first site of recurrence for patients.
- (3) To estimate the influence of concurrent and consolidative MK-3475 on levels of plasminogen activator inhibitor-1 (PAI-1), a marker of immunosuppressive TGF-B.
- (4) To estimate the influence of concurrent and consolidative MK-3475 on levels of IDO, an enzyme that depletes tryptophan, which is essential for T-cell function.
- (5) To estimate the influence of concurrent and consolidative MK-3475 on levels of MHC class I (CD8+ T cell ligand) and MICA (NK ligand), as measured by MHC.
- (6) To estimate the progression free survival (PFS) in subjects with locally advanced cervical cancer treated with sequential and concurrent administration of pembrolizumab in relation to CRT.
- (7) To estimate the overall survival (OS) in subjects with locally advanced cervical cancer treated with sequential and concurrent administration of pembrolizumab in relation to CRT.

## 4.0 BACKGROUND & RATIONALE

## 4.1 Disease Background

Cervical cancer is the fourth most common cancer among women worldwide, with an estimated 528,000 new cases and 266,000 deaths in 2012.[1] The standard of care (SOC) for patients with locally advanced cervical cancer (LACC) is concurrent chemoradiation therapy (CRT) with weekly cisplatin.[2] Five-year disease OS after contemporary CRT for Stages IB-IVA cervical cancer is only 66%.[2]

Human Papillomavirus (HPV) DNA is detected in virtually all cervical cancers, and HPV specific CD4+ and CD8+ T cells are found in cervical tumors.[3] The failure of the immune system to eradicate HPV DNA integration is due to cancer cells' acquisition of cytotoxic T cells, including down-regulation of HLA class I, down-regulation of MHC class I chain-related molecule A (MICA), production of immunesuppressive cytokines, and induction of FoxP3+ immunosuppressive regulatory T cells.[4] Low ratios of CD8+ T cells: regulatory T cells (Tregs) are associated with poorer survival for cervical cancer patients,[4] suggesting that strategies to enhance immune response would be effective.

Compelling evidence indicates that B7 molecules (i.e., B7-1/CD80, B7-2/CD86, B7-H1/PDL1, B7-H2/LICOS, B7-DC, B7-H3 and B7-H4) and their ligands (i.e., CTLA-4, CD28, PD-1, ICOS) not only provide crucial positive signals to stimulate and support T-cell activation, but also offer negative signals that control and suppress potentially protective T-cell responses against spontaneously arising and virally-induced human tumors.[5] Expression of these molecules on the surface of cervical tumor cells, tumor associated macrophages, and/or dendritic cells (DC), may attenuate or abrogate the ability of the immune system to eliminate strongly antigenic (i.e., virus-infected) tumors such as cervical cancer.[5] Because these negative signals in human solid tumors have been shown to be largely provided by programmed death, blockade of PD- 1/PD-L1 co-inhibitory pathways by novel monoclonal antibodies may represent an innovative and effective approach to reverse immune suppression while inducing tumor-specific immunity in cervical cancer patients.

PD-1 and PD-L1 expression on cervical T cells and DCs, respectively, has been recently reported to be associated with high risk-HPV positivity and to be increased in parallel with increasing CIN grade.[6] Increased expression of PD-1 and PD-L1 correlates with impaired cell-mediated immunity in high-risk HPV related CIN.[7] Finally, in cervical cancer, PD-1 is expressed by the majority of infiltrating CD8 T cells, suggesting that blocking of PD-1 could have therapeutic potential.[7] Taken together, this evidence validates the importance of the PD-1-PD-L1 pathway for the treatment of patients harboring virally-infected tumors such as cervical cancer.

# 4.2 Pembrolizumab

Refer to the Investigator's Brochure (IB)/approved labeling for detailed background information on pembrolizumab.

# 4.2.1 Pharmaceutical and Therapeutic Background

The importance of intact immune surveillance in controlling outgrowth of neoplastic transformation has been known for decades. Accumulating evidence shows a correlation between tumor-infiltrating lymphocytes (TILs) in cancer tissue and favorable prognosis in various malignancies. In particular,

the presence of CD8+ T-cells and the ratio of CD8+ effector T-cells / FoxP3+ regulatory T-cells seems to correlate with improved prognosis and long-term survival in many solid tumors.

The PD-1 receptor-ligand interaction is a major pathway hijacked by tumors to suppress immune control. The normal function of PD-1, expressed on the cell surface of activated T-cells under healthy conditions, is to down-modulate unwanted or excessive immune responses, including autoimmune reactions. PD-1 (encoded by the gene Pdcd1) is an Ig superfamily member related to CD28 and CTLA-4 which has been shown to negatively regulate antigen receptor signaling upon engagement of its ligands (PD-L1 and/or PD-L2). The structure of murine PD-1 has been resolved. PD-1 and family members are type I transmembrane glycoproteins containing an Ig Variable-type (V-type) domain responsible for ligand binding and a cytoplasmic tail which is responsible for the binding of signaling molecules. The cytoplasmic tail of PD-1 contains 2 tyrosine-based signaling motifs, an immunoreceptor tyrosine-based inhibition motif (ITIM) and an immunoreceptor tyrosine-based switch motif (ITSM). Following T-cell stimulation, PD-1 recruits the tyrosine phosphatases SHP-1 and SHP-2 to the ITSM motif within its cytoplasmic tail, leading to the dephosphorylation of effector molecules such as CD3ζ, PKC0 and ZAP70 which are involved in the CD3 T-cell signaling cascade. The mechanism by which PD-1 down modulates T-cell responses is similar to, but distinct from that of CTLA-4 as both molecules regulate an overlapping set of signaling proteins. PD-1 was shown to be expressed on activated lymphocytes including peripheral CD4+ and CD8+ T-cells, B-cells, T regs and Natural Killer cells. Expression has also been shown during thymic development on CD4-CD8-(double negative) T-cells as well as subsets of macrophages and dendritic cells. The ligands for PD-1 (PD-L1 and PD-L2) are constitutively expressed or can be induced in a variety of cell types, including non-hematopoietic tissues as well as in various tumors. Both ligands are type I transmembrane receptors containing both IgV- and IgC-like domains in the extracellular region and contain short cytoplasmic regions with no known signaling motifs. Binding of either PD-1 ligand to PD-1 inhibits Tcell activation triggered through the T-cell receptor. PD-L1 is expressed at low levels on various nonhematopoietic tissues, most notably on vascular endothelium, whereas PD-L2 protein is only detectably expressed on antigen-presenting cells found in lymphoid tissue or chronic inflammatory environments. PD-L2 is thought to control immune T-cell activation in lymphoid organs, whereas PD-L1 serves to dampen unwarranted T-cell function in peripheral tissues. Although healthy organs express little (if any) PD-L1, a variety of cancers were demonstrated to express abundant levels of this T-cell inhibitor. PD-1 has been suggested to regulate tumor-specific T-cell expansion in subjects with melanoma (MEL). This suggests that the PD-1/PD-L1 pathway plays a critical role in tumor immune evasion and should be considered as an attractive target for therapeutic intervention.

Pembrolizumab is a potent and highly selective humanized monoclonal antibody (mAb) of the IgG4/kappa isotype designed to directly block the interaction between PD-1 and its ligands, PD-L1 and PD-L2. Keytruda™ (pembrolizumab) has recently been approved in the United Stated for the treatment of patients with unresectable or metastatic melanoma and disease progression following ipilimumab and, if BRAF V600 mutation positive, a BRAF inhibitor.

